#### **6.4 Concomitant Therapy**

Throughout the study, investigators may prescribe any concomitant medications or treatments deemed necessary to provide adequate supportive care except for those listed in [Section 6.7](#).

An attempt should be made not to change the subjects' treatment during the course of the study as long as, in the judgment of the investigator, the subjects' safety is not jeopardized. All use of concomitant medications and supplements will be recorded on the applicable CRF. Concomitant therapies are to be collected from informed consent through the end of safety follow-up period. Collect therapy name, indication, dose, unit, frequency, route, and start date and stop date.

In cases of symptomatic hypocalcemia or if the serum calcium level is less than 7.5 mg/dL (1.875 mmol/L), oral or IV calcium will be administered as necessary.

All herbal supplements, vitamins, and nutritional supplements taken within the last 30 days prior to dosing on Day 1 (and continued use, if appropriate) must be reviewed and approved by the Principal Investigator and Amgen Medical Monitor.

#### **6.5 Other Treatment Procedures - Haemodialysis**

Haemodialysis information - including date(s), mode of dialysis, start and stop times - and the dialysate (amount of calcium and potassium) must be captured in the subject's chart and reported on the appropriate case report form.

#### **6.6 Product Complaints**

A product complaint is any written, electronic or oral communication that alleges deficiencies related to the identity, quality, durability, reliability, safety, effectiveness, or performance of a drug(s) or device(s) after it is released for distribution to market or clinic by either Amgen or by distributors and partners for whom Amgen manufactures the material. This includes any drug(s) or device(s) provisioned and/or repackaged /modified by Amgen. Drug(s) or device(s) includes investigational product.

Any product complaint(s) associated with etelcalcetide supplied by Amgen are to be reported according to the instructions provided in the IPIM.

#### **6.7 Excluded Treatments, Medical Device Use, and/or Procedures During Study Period**

Treatment with cinacalcet is prohibited within 30 days prior to receiving etelcalcetide and for the duration of the study. Use of any medications that prolong QT interval (eg, sotalol, amiodarone, erythromycin, or clarithromycin) within 28 days prior to receiving

etelcalcetide and for the duration of the study is prohibited. Please refer to the complete QT prolongation medication list at

<http://www.crediblemeds.org/pdftemp/pdf/CompositeList.pdf>. These excluded therapies and procedures will not be allowed during the study unless necessitated in order to maintain subject safety.

**7. STUDY PROCEDURES**

**7.1 Schedule of Assessments**

**Table 1. Schedule of Assessments**

	Screening	Baseline		Treatment		Follow up			EOS	
Study Day	-14 to -3	-2		1		3	5 a	8	10	30
Study Time			0	10 min	4 hour					
General and Safety Assessments										
Informed consent	X									
Medical history	X									
Weight (kg)	X	X								X
Height (cm)	X									
Vital signs (BP, HR, Temp)	X	X								X
Physical examination	X									X
12-lead ECG	X	X								X
Serious adverse events			X-----X							
Adverse Events				X-----X						
Concomitant medications			X-----X							
Dosing										
Etelcalcetide administration b			X							
Laboratory Assessments										
Clinical chemistry	X									X
Hematology	X									X
Ionized Ca, Serum albumin, Serum cCa c, d	X	X			X	X		X	X	X
Serum PTH c	X	X			X	X		X	X	X
Serum pregnancy test (females of child bearing potential only) e	X									
Pharmacokinetic and Other Blood Samples										
Etelcalcetide PK plasma collection c, f			X	X	X f	X	X	X	X	X
Antibody sample collection g		X								X

Footnotes defined on next page of table

cCa = albumin-corrected calcium; EOS = End of Study; iCa = ionized calcium; HD = haemodialysis; IV = intravenous

- a. Subjects will continue to receive HD per their regular schedule (Day -2, 1, 3, 5 [or Day 6 depending on the day of the week the study begins], 8 and 10).
- b. On Day 1, etelcalcetide will be administered as an IV bolus dose after HD during rinse back.
- c. All procedures (except those scheduled on Day 1 at time 0, 10 min and 4 hour and Day 3 post-HD) will be performed prior to HD on the respective study day.
- d. Serum samples for albumin and calcium for screening and routine monitoring of pre-HD cCa. When albumin is less than 4.0 mg/dL, the calcium level will be corrected according to the formula:  $cCa \text{ (mg/dL)} = \text{total Ca (mg/dL)} + (4 - \text{albumin (g/dL)}) * 0.8$ .
- e. Pregnancy tests will be performed in female subjects of child-bearing potential within 7 days prior to start of investigational product.
- f. PK plasma collection pre-HD and post-HD on Day 3
- g. Subjects with positive titers for antibodies to etelcalcetide at EOS may be asked to return to the clinical research unit to provide additional serum samples.

## 7.2 General Study Procedures

During the study, every effort should be made to perform the study procedures as indicated in the Schedule of Assessments ([Table 1, Section 7.1](#)). Study visits should coincide with the subject's haemodialysis (HD) schedule. Unless otherwise noted all procedures should be performed prior to HD (pre-HD). Depending on the day of the week that each subject begins the study (Day 1), Day 5 assessments may be performed on Day 6 to align with the subject's HD schedule.

Throughout the study, the permitted time windows for scheduled assessments will be as follows:

- $\pm$  15 minutes for events on Day 1
- $\pm$  30 minutes for Day 3 through 10
- +1 day for Day 5
- + 3 days for Day 30 (EOS)

Additional procedures deemed necessary as part of standard of care or as required by local laws and regulations may be performed at the Investigator's discretion.

Key assessments are described in the subsections below.

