### 2.2.2 Clinical Pharmacokinetics

In the adult population, the pharmacokinetics of etelcalcetide are linear and does not change over time following single (5 to 60 mg) and multiple IV doses (2.5 to 20 mg) in CKD patients with secondary HPT requiring haemodialysis. Etelcalcetide exhibited tri-exponential decay following IV administration. Following three times a week IV dosing at the end of each 3 to 4 hour haemodialysis session in adult CKD patients, etelcalcetide plasma levels reached near steady-state after 4 weeks of dosing with an observed accumulation ratio of 2- to 3-fold, and the effective half-life was 3 to 5 days when dosed three times a week following hemodialysis. Etelcalcetide is rapidly cleared in patients with normal renal function, while haemodialysis is the predominant elimination pathway in CKD patients requiring haemodialysis.

Etelcalcetide is not metabolized by CYP450 enzymes. Etelcalcetide is predominately bound to plasma albumin by reversible covalent binding. In adult CKD patients requiring haemodialysis, etelcalcetide was predominantly eliminated by haemodialysis.

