## 3. EXPERIMENTAL PLAN

### 3.1 Study Design

This is a single arm, open-label, single-dose safety, pharmacokinetic (PK) and pharmacodynamic (PD) study in paediatric subjects with sHPT receiving maintenance haemodialysis. The study considers haemodiafiltration and haemodialysis procedures interchangeable. Subjects will receive a single IV administration of 0.035 mg/kg etelcalcetide at the end of haemodialysis. Intensive PK and PD samples will be collected on Day 1 at 10 min and 4 hours after etelcalcetide administration and for 10 days post dose with a safety follow-up period up to 30 days post dose.

The overall study design is described by a [study schema](#) at the end of the protocol synopsis section.

The study endpoints are defined in [Section 10.1.1](#)

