#### 7.2.4 Treatment

The following procedures will be completed during the treatment period at the times designated in the Schedule of Assessments ([Table 1](#)). On Day 1 etelcalcetide is to be administered after the completion of all required pre-dose assessments and after HD, during rinse back. Subjects will remain in the clinical research unit for observation until the 4 hour PK sample is collected.

- Etelcalcetide administration
- PK (10 min and 4 hour post dose)
- Laboratory assessments (pre-HD)
- Serious Adverse Event reporting
- Adverse Event reporting
- Documentation of concomitant medications

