### **7.2.13 Pharmacokinetic Measurements**

Blood samples (0.15 mL) for the determination of etelcalcetide PK parameters will be collected at time points designated in the Schedule of Assessments. Study site staff will complete a shipping log that will include subject identification information and the time and date of collection of each sample. Detailed instructions on sample collection, storage and shipment to the central laboratory are provided in a separate Sample Collection Notebook.

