#### **10.4.3 Secondary Endpoint(s)**

##### **10.4.3.1 Pharmacokinetic Endpoints**

Etelcalcetide concentration-time data in plasma will be used to determine the PK parameters using non-compartmental methods. Plasma etelcalcetide concentrations below the lower limit of quantifications will be set to zero for the estimation of the pharmacokinetic parameters for each subject and for the calculation of the summary statistic for each time point. Actual dosing and sampling time will be used for all calculations. The reasons for excluding any sample from the analyses will be provided.

Individual and mean (SE) plasma concentration-time data for etelcalcetide will be presented graphically. PK parameters will be summarized for all subjects using descriptive statistics.

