###### **Secondary Endpoints:**

- Pharmacokinetic parameters (AUC, Cmax, tmax, t1/2) of etelcalcetide in plasma
- Pharmacodynamics: concentration of parathyroid hormone (PTH), serum calcium [total calcium, ionized calcium and albumin corrected calcium] over time
- Anti-etelcalcetide antibodies
- Incidence of treatment-emergent adverse events

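### The Day 1 time window (plus or minus 15 minutes) is wider than the nominal time of the 10-minute PK sample, so draws from 5 minutes before to 25 minutes after the bolus comply, and this sample is expected to set observed Cmax

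*Protocol*

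**What the plan says.** Protocol Section 7.2 sets the permitted windows for scheduled assessments. For Day 1 there is one entry, plus or minus "15 minutes for events on Day 1", and it names no exception.

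Protocol Section 3.1 (repeated in SAP Section 3.1) fixes the Day 1 times: "Intensive PK and PD samples will be collected on Day 1 at 10 min and 4 hours after etelcalcetide administration". Section 7.2.4 lists the same two draws as "PK (10 min and 4 hour post dose)". Table 1 also has a PK draw at time 0, in the same column as dosing. Section 7.2.4 does not count it as post dose, so I take it as a pre-dose sample.

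On dosing, footnote b of Table 1 says: "On Day 1, etelcalcetide will be administered as an IV bolus dose after HD during rinse back". On disposition in adults, Protocol Section 2.2.2 says: "Etelcalcetide exhibited tri-exponential decay following IV administration". It gives an effective half-life of 3 to 5 days under three-times-weekly dosing, but no half-life or weight for the early phases.

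The SAP lists as a secondary endpoint: "Pharmacokinetic parameters (AUC, Cmax, tmax, t1/2) of etelcalcetide in plasma". The glossary defines Cmax as the maximum plasma concentration. Protocol Section 10.4.3.1 says: "Actual dosing and sampling time will be used for all calculations". SAP Section 10.6.2 agrees and specifies non-compartmental analysis. Neither document states a rule for back-extrapolating a concentration at time zero (C0).

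Protocol Section 7.2.13 requires the time of each sample to be logged and adds: "Detailed instructions on sample collection, storage and shipment to the central laboratory are provided in a separate Sample Collection Notebook". That notebook is not among the documents.

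**The concern.** A tolerance of 15 minutes is small for a 4-hour sample and large for a 10-minute one. After an IV bolus the concentration is expected to fall from the start, so the first post-dose sample should be the highest and its value becomes observed Cmax. Two subjects with the same concentration curve, one drawn at 5 minutes and one at 25, would both comply and would report different Cmax values.

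What is at stake is comparability. Cmax is described in cohorts that may hold as few as 5 subjects each (Protocol Section 3.3). Part of the spread, or of an apparent difference between age cohorts, could reflect when the sample was taken. A compliant draw at 25 minutes would not be recorded as a timing deviation.

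The lower limit has a separate flaw: a window that opens before the dose does not fit a sample listed as post dose.

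**Working it through.** The plan states no expected Cmax or precision, so there is no figure of its own to reproduce.

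**Step 1: window limits (document figures only).**
- 10-minute sample: 10 - 15 = -5 min and 10 + 15 = +25 min. Tolerance over nominal time: 15/10 = 150%.
- 4-hour sample: 240 - 15 = 225 min and 240 + 15 = 255 min. Tolerance over nominal time: 15/240 = 6.25%.

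**Step 2: what actual times do.**
- tmax: if the first post-dose sample is the highest, tmax on actual times is simply the draw time. It is recorded truthfully but not moved towards the real peak.
- Cmax: it is the measured concentration, so no adjustment takes place.
- AUC: each point sits at its true time, but a later first point leaves more of the early curve unobserved. With no stated C0 rule, AUC is only partly protected.

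**Step 3: size of a late draw.** The early half-life h is an assumption: 30, 60 or 240 min. Two shapes are used:
- one phase: C(t)/C(10) = 2^(-(t-10)/h);
- half flat: C(t)/C(10) = 0.5 + 0.5 × 2^(-(t-10)/h), which assumes that half of the 10-minute level belongs to slower phases that barely move over these minutes.

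One late draw among 5 subjects, the others drawn at 10 min and otherwise equal, lowers mean Cmax by (1 - C(25)/C(10))/5.

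| Quantity | Shape | h = 30 | h = 60 | h = 240 |
|---|---|---|---|---|
| C(25)/C(10) | one phase | 0.707 | 0.841 | 0.958 |
| C(25)/C(10) | half flat | 0.854 | 0.920 | 0.979 |
| Fall in mean, 1 late of 5 | one phase | 5.9% | 3.2% | 0.8% |
| Fall in mean, 1 late of 5 | half flat | 2.9% | 1.6% | 0.4% |

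**Step 4: spread from draw time alone.** This is the coefficient of variation (CV) of C(t)/C(10) with t uniform over the stated range. The range 1 to 25 min is the post-dose part of the present window and is an upper case, since Section 7.2 asks sites to make every effort to keep the schedule.

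| Draws spread over | Shape | h = 30 | h = 60 | h = 240 |
|---|---|---|---|---|
| 1 to 25 min | one phase | 16% | 8% | 2% |
| 1 to 25 min | half flat | 7.8% | 3.9% | 1.0% |
| 5 to 15 min | one phase | 6.7% | 3.3% | 0.8% |
| 5 to 15 min | half flat | 3.3% | 1.7% | 0.4% |

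**Step 5: outer bounds.** A faster early phase enlarges the effect: with one phase and h = 10 min, C(25)/C(10) = 2^(-15/10) = 0.35. If only the 3 to 5 day half-life applied (4,320 to 7,200 min), the ratio would be 2^(-15/4320) = 0.998 to 2^(-15/7200) = 0.999, which is negligible. The statement of tri-exponential decay means that this half-life alone does not describe the curve.

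**The case against.** The strongest reply is that little rests on this. All analyses are descriptive (SAP Section 5), so no test is affected. The Cohort 2 review looks at PK results (Protocol Section 6.2.1.2, SAP Section 8) but sets no Cmax criterion. A reader might infer that the window could mislead the decision to open Cohort 2; the documents do not support that. This stands and keeps the point minor.

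Second, the size is assumed throughout, and one-phase decay overstates it if a large part of the early level belongs to slower phases. It may also be small beside ordinary variation. With an assumed between-subject CV of 30% (the documents give none), a draw-time CV of 16% raises the total to √(0.30² + 0.16²) = 34%, and 8% raises it to 31%. This also stands, which is why both shapes are shown.

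Third, draw time is already captured: it is logged, and tmax on actual times would equal it. So a draw-time listing is largely a matter of setting tmax beside Cmax for each subject. A reader might go further and infer that actual times cure the problem. They do not, because they leave the measured Cmax unchanged.

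Fourth, the Sample Collection Notebook may already set a tighter limit. That cannot be checked here. If it does, the notebook and Section 7.2 differ and should be aligned.

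Fifth, a narrow window needs a clear time zero. The dose goes in during rinse back. The documents give no rinse-back duration and do not say whether the clock starts at the start or the end of the bolus. This is a fair point against a very tight window, and the fix takes it up.

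**Conclusion.** The point holds as a minor design improvement. It is exact on the text that the 10-minute sample is in window from -5 to +25 minutes, and that the lower limit does not fit a post-dose sample. It is a sound inference, not a stated fact, that this sample will set observed Cmax.

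The effect on Cmax is unknown. Over assumed early half-lives of 30 to 240 minutes, a 25-minute draw reads 71% to 96% of the 10-minute level with one phase, or 85% to 98% if half the level is flat. It could be larger with a faster early phase, or negligible if the early phases carry little of the level.

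Two stronger readings should be resisted. One is that pre-dose draws are intended or likely: the negative limit follows only from applying a general window literally, and Section 7.2.4 shows the intent. The other is that the window causes the study to miss the peak: a draw at exactly 10 minutes would also come after the true peak of a bolus. A tighter window makes subjects more comparable and does no more than that.

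**What to change.** In Protocol Section 7.2, give the 10-minute PK sample its own window, strictly post dose and clearly shorter than 10 minutes, for example plus or minus 5 minutes (5 to 15 minutes after dosing). State whether time zero is the start or the end of the bolus. Keep plus or minus 15 minutes for the 4-hour sample. If the Sample Collection Notebook is already tighter, align Section 7.2 with it.

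In SAP Section 10.6.2, list each subject's Cmax beside tmax (the actual draw time). Flag 10-minute samples outside the window and keep them in the analysis at their actual time.

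The cost is one protocol line, one SAP sentence and a listing, with no added samples or visits. A few more timing deviations will be recorded. The protocol line needs investigator agreement and IRB/IEC approval (Protocol Section 12.1) at about 15 sites (Section 3.2), so it is best combined with another amendment. The SAP listing need not wait for it.

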### 7.2.1 Informed Consent

Before any study-specific procedure, the appropriate written informed consent must be obtained from the subject's legally acceptable representative.

### 7.2.2 Screening

The following procedures are to be completed during the screening period at time points designated in the Schedule of Assessments ([Table 1](#)) ([Section 7.1](#)).

- Confirmation that the Informed Consent Form and Assent form (as applicable) have been signed
- Demographic data including sex, age, race, and ethnicity will be collected in order to study their possible association with subject safety
- Physical Examination as per standard of care (including medical/surgical history)
- Height and Weight
- Vital signs (eg, blood pressure, heart rate, temperature) (pre-HD)
- 12-Lead ECG (pre-HD)
- Laboratory assessments (pre-HD)
- Serious Adverse Event reporting
- Documentation of concomitant medications

If a subject is rescreened, a new informed consent form must be signed unless it has been < 30 days since the previous ICF signature was obtained.

#### 7.2.3 Baseline

Two days before dosing (Day -2) eligible subjects will return to the research center for testing to confirm final eligibility and to establish baseline assessments prior to dosing.

The following procedures will be completed at baseline and at time points designated in the Schedule of Assessments ([Table 1](#)) ([Section 7.1](#)).

- Weight
- Vital signs (eg, blood pressure, heart rate, temperature) (pre-HD)
- 12-Lead ECG (pre-HD)
- Laboratory assessments (pre-HD)
- Anti-etelcalcetide antibody collection (pre-HD)
- Serious Adverse Event reporting
- Documentation of concomitant medications

After the investigator has confirmed eligibility based on screening and Day -2 assessments, the subject will be enrolled to Cohort 1 or Cohort 2 based on the subject's age.

#### 7.2.4 Treatment

The following procedures will be completed during the treatment period at the times designated in the Schedule of Assessments ([Table 1](#)). On Day 1 etelcalcetide is to be administered after the completion of all required pre-dose assessments and after HD, during rinse back. Subjects will remain in the clinical research unit for observation until the 4 hour PK sample is collected.

- Etelcalcetide administration
- PK (10 min and 4 hour post dose)
- Laboratory assessments (pre-HD)
- Serious Adverse Event reporting
- Adverse Event reporting
- Documentation of concomitant medications

#### 7.2.5 Safety Follow-up Visit(s)

Safety follow up visits will occur on Day 3, 5 or 6 (depending on study start day), 8 and 10. The following procedures will be completed at the safety follow-up visits according to the Schedule of Assessments ([Table 1](#)).

- PK assessments (pre-HD and post-HD on Day 3; pre-HD on Day 5 or 6, Day 8 & Day 10)
- Laboratory Assessments (pre-HD)
- Serious Adverse Event reporting
- Adverse Event reporting
- Documentation of concomitant medications

#### **7.2.6 End of Study Visit**

The end of study visit will occur on Day 30. The following procedures will be completed at the safety follow-up visits according to the Schedule of Assessments ([Table 1](#)).

- Physical Examination as per standard of care
- Weight
- Vital signs (eg, blood pressure, heart rate, temperature) (pre-HD)
- 12-Lead ECG (pre-HD)
- PK assessments (pre-HD)
- Laboratory Assessments (pre-HD)
- Anti-etelcalcetide antibody collection (pre-HD)
- Serious Adverse Event reporting
- Adverse Event reporting
- Documentation of concomitant medications

#### **7.2.7 Medical History**

The investigator or qualified designee will obtain a complete medical history at screening and within 14 days prior to enrollment of a study subject. Medical history will include the subject's history of chronic kidney disease and secondary hyperparathyroidism.

Relevant medical history findings will be recorded in the subject's source document and on the appropriate CRF. Any unresolved medical history will be graded according to Common Terminology Criteria for Adverse Events (CTCAE) version 4.0 ([Appendix A](#)).

#### **7.2.8 Vital Signs**

Vital signs, including systolic/diastolic blood pressure, heart rate, and temperature will be recorded by the investigator or qualified designee at the time points specified in the Schedule of Assessments ([Table 1](#)). All measurements will be obtained prior to hemodialysis.

Subjects must be in a supine position for at least 5 minutes prior to vital signs measurements. Abnormal measurements may be repeated (upon investigator discretion) and must be reported on the CRF. When vital signs and blood sample

collection occur at the same time, vital signs should be performed before blood samples are drawn. The position selected for a subject should be the same that is used throughout the study and documented on the vital sign CRF. The temperature location selected for a subject should be the same that is used throughout the study.

Record all measurements on the vital signs CRF.

